#### Safety Analysis and Stopping Rules for Excessive Toxicity

The following table will be consulted as relevant toxicities are encountered. The early stopping rule for safety/toxicity will be assessed for each patient after 3 weeks of treatment. The expected rate of unacceptable toxicity should not be  $\geq 33\%$ . See the table below for detailed early stopping rules. These rules are in addition to the quarterly review of all toxicities submitted to the COH DSMC. Patients with ongoing toxicity (toxicity persisting beyond day +21) will be followed until resolution or stability. If more than the specified number of patients has significant treatment related toxicities, patient accrual will be halted and a full review of the data by the Data Safety Monitoring Committee (DSMC) will be mandated. Patient accrual will not resume until approved by the DSMC to do so.

# of patients treated at phase II dose	# of patients with unacceptable toxicity to halt enrollment 	# of patients expired due to treatment related causes that would stop the study 	Given the following toxicity rates, cumulative probability of early stopping:		
			15%	33%	45%
6	2	2	0.22	0.64	0.84
9	3	3	0.25	0.72	0.89
12	4	4	0.26	0.75	0.93
18	6	6	0.27	0.80	0.95

: For each unacceptable toxicity, halt enrollment and evaluate if the cumulative # of patients reaches or exceeds the specified limits.

: Expected treatment related mortality should not exceed 33%.

In addition, cumulative safety data will be reviewed on a quarterly basis in order to identify safety concerns that may emerge due to cumulative exposure.

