### **5.3 Planned Duration of Therapy:**

IL-2 and ECP combination therapy will be given for 12 weeks, with final immune assessment occurring at 16 weeks post-initiation of therapy. Patients deemed to be benefiting from combination therapy (i.e. in complete remission, partial remission, minor response or stable disease), will have the options to continue onto the extended duration per discretion of treating physician.

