### 6.2 Extracorporeal photopheresis:

The incidence of ECP reported side effects is extremely low at less than 0.003% especially in cGVHD patient population. The procedural risks with new third generation ECP devices is even smaller. Many of the complications attributable to ECP are related to vascular access. It would be preferable to use peripheral veins, but patients with cGVHD frequently have poor veins, and alternative access must therefore be used. When central venous catheters are used, complications such as infection, clotting in the catheters, deep venous thrombosis, and vessel stenosis can occur.

For this study, modifications of ECP therapy as described below are required for patients in the first 12 weeks of study. Infection: Of note, infection during ECP+ IL-2 treatment is not considered intervention-related, since both cGVHD and the concurrent use of immune suppression medications are known risk

factors for infection. Infection is therefore considered an expected complication of cGVHD. However, patients who develop a CTC grade 3 or higher infection prior to week 12 of ECP+ IL-2 therapy will have therapy withheld during active infection. They can be considered for restarting ECP after control of infection, at the discretion of the treating physician. CVP line infection and bacteremia/sepsis requiring line removal will result in temporary stoppage of ECP therapy.

- Severe (grade-4) hematologic toxicity: ECP+IL-2 will be withheld for severe declines in peripheral counts (ANC<500, Plts<10,000) not related to malignant disease relapse, infection or other etiologies. If counts improve (ANC>1000, Plts>20,000) within 2 weeks, ECP will be restarted per schedule. If peripheral counts do not improve within 2 weeks, or drop again (ANC<500, Plts<10,000) after restarting ECP + IL-2, it will be discontinued. Use of myeloid growth factors and transfusion of platelet and PRBC's will be per standard institutional guidelines and is allowed while patients are on trial.

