### 11.2 Secondary Endpoints

##### **Toxicity:**

Toxicity will be graded according to the NCI-Common Terminology Criteria for Adverse Events version 4.03. Unacceptable toxicity will be defined as any toxicities that are at least possibly related to either ECP or IL-2 and occur during cycle 1 (within 10 days of initiation of therapy).

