### 13.1 Study Design, Sample Size, and Accrual Rate

This single center/single arm, phase II clinical trial is designed to evaluate the anti-cGVHD activity of extracorporeal photopheresis (ECP) when combined with low dose IL-2, in patients with steroid refractory cGVHD, as assessed by overall cGVHD response rate (CR+PR+SD). The primary endpoint overall response (CR+PR+SD) is based on the NIH cGVHD consensus criteria; calculated as the percent of evaluable patients that have confirmed CR/PR or SD

This study will implement a Simon, optimal, two-stage design to evaluate the anti-cGVHD activity of the ECP/IL-2 regimen. The trial is expected to enroll 24 patients e sample size is based on the desire to discriminate a promising response rate of 50% from a current response rate of 25%. The null hypothesis

that the true response rate is 25% will be tested against a one-sided alternative. In the first stage, 9 patients will be accrued. If there are 2 or fewer responses in these 9 patients, the study will be stopped. Otherwise, 15 additional patients will be accrued for a total of 24. The null hypothesis will be rejected if 10 or more responses are observed in 24 patients. This design yields a type I error rate of 0.05 and power of .80 when the true response rate is 50%. Currently, about 20-25 new patients are referred to ECP per year. We expect that 6 patients to be enrolled per year with the expected completion of accrual in 4 years.

**Evaluable for Response:** As part of the primary analysis, patients will be considered evaluable for response if they are eligible, have baseline disease assessments, and receive protocol treatment of any duration. All such patients will be evaluated for clinical response. Our primary outcome will be the clinical response rate measured in all patients who are enrolled and receive any amount of protocol therapy.

Patients who are consented for the study but withdraw for any reason (progression of GVHD, infectious complications, insurance denial etc) prior to initiation of protocol therapy will not be eligible for response evaluation.

**Evaluable for Toxicity:** Patients will be considered evaluable for toxicity if they receive any study drug.

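### The toxicity rule that halts accrual counts an ungraded event confined to the first 10 days, so its printed stopping probabilities do not describe the 12-week course

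*Combined protocol and SAP*

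**What the plan says.** The table under *Safety Analysis and Stopping Rules for Excessive Toxicity* (13.1) sets limits on patients with *unacceptable toxicity*: 2 of 6, 3 of 9, 4 of 12 and 6 of 18. A second column sets the same limits for treatment-related deaths. On timing, the text says: "The early stopping rule for safety/toxicity will be assessed for each patient after 3 weeks of treatment".

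Section 13.1 does not define the counted event or point to a definition. The term is defined once, in 11.2: "Unacceptable toxicity will be defined as any toxicities that are at least possibly related to either ECP or IL-2", provided that they "occur during cycle 1 (within 10 days of initiation of therapy". No grade is given, and the trial has no cycles. Section 13.1 also uses two undefined descriptions, *relevant* toxicities and, for the action itself, "has significant treatment related toxicities, patient accrual will be halted".

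On the threshold, the body text requires more than the listed number, while footnote 1 halts when the count reaches or exceeds it.

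On treatment length, 5.3 says "IL-2 and ECP combination therapy will be given for 12 weeks". For later harms, 13.1 adds that "cumulative safety data will be reviewed on a quarterly basis in order to identify safety concerns that may emerge due to cumulative exposure". Sections 5.5, 6.1 and 6.2 give patient-level rules, for example "Severe (grade-4) hematologic toxicity: ECP+IL-2 will be withheld for severe declines in peripheral counts".

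**The concern.** A numeric stopping rule works only if everyone counts the same events over the same period. Here the only available definition is too wide in severity and too narrow in time. Followed literally, a grade 1 injection-site reaction on day 5 moves the trial towards a halt. A related, non-fatal grade 4 event in week 6 does not.

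The printed probabilities and the 33% ceiling then describe the rate inside a short window, while a reader will take them as protection over the whole 12-week course. The documents do not suggest that the important harms end early. Section 8.1.3 expects thrombotic microangiopathy in 7% of patients, 8.2.1 lists line infection and line thrombosis, and ECP continues to week 11.

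**Working it through.** **Inputs.** Limits, footnote 1 and printed probabilities: table in 13.1. Window of 10 days: 11.2. Assessment at 3 weeks (21 days): 13.1. Treatment of 12 weeks (84 days): 5.3. Accrual: "We expect that 6 patients to be enrolled per year" (13.1).

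**Step 1. Reproduce the table.** Let p be the probability that a patient is counted, and halt at a look if the cumulative count is at or above the limit. At the first look with p = 0.33:

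P(X ≥ 2 of 6) = 1 − 0.67⁶ − 6 × 0.33 × 0.67⁵ = 1 − 0.0905 − 0.2673 = 0.642 (printed 0.64).

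For later looks, carry forward the distribution of counts still below the limit, add the binomial count of the next 3, 3 and 6 patients, and accumulate the probability at or above each limit.

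| Rate | Computed at 6 / 9 / 12 / 18 | Printed |
|---|---|---|
| 15% | 0.224 / 0.249 / 0.260 / 0.264 | 0.22 / 0.25 / 0.26 / 0.27 |
| 33% | 0.642 / 0.714 / 0.753 / 0.792 | 0.64 / 0.72 / 0.75 / 0.80 |
| 45% | 0.836 / 0.897 / 0.927 / 0.956 | 0.84 / 0.89 / 0.93 / 0.95 |

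All twelve cells agree within 0.01, so the table is sound under footnote 1. The body-text rule (limits 3/6, 4/9, 5/12, 7/18) gives 0.313 / 0.407 / 0.468 / 0.536 at 33%, which does not match.

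**Step 2. Effect of the window.** Let P be the 12-week rate and f the share of affected patients whose event falls in the counted window, so p = f × P. The documents do not give f, so it is an assumption. Probability of a halt by 18 patients:

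| f | P = 33%: p, halt | P = 45%: p, halt |
|---|---|---|
| 50% | 0.165, 0.31 | 0.225, 0.50 |
| 75% | 0.2475, 0.57 | 0.3375, 0.81 |
| 90% | 0.297, 0.71 | 0.405, 0.91 |
| 100% | 0.33, 0.79 | 0.45, 0.96 |

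If events were instead spread evenly (constant hazard), p = 1 − (1 − P)^(d/84) for a window of d days:

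- P = 33%: a 10-day window gives p = 0.047 and a halt probability of 0.03. A 21-day window gives p = 0.095 and 0.12.
- P = 45%: the halt probabilities are 0.06 (10 days) and 0.23 (21 days).

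**Step 3. What covers the rest of the course.** At 6 patients per year, a quarterly review comes about every 6/4 = 1.5 new patients. About 6 × 84/365 = 1.4 patients are on treatment at any time. The review has no numeric limit. The death column has one, and neither that column nor footnote 2 restricts it in time.

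**The case against.** The strongest reply is that the text can be read sensibly and that little is exposed. Several parts of it stand, and they rule out stronger readings that a reader might draw.

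- *That the 10-day and 3-week times contradict each other.* They need not. One can be when the event occurs and the other when the patient is scored. The text does not say so, but it does not exclude it. On that reading everything after day 10 is still uncounted.
- *That nothing numeric can stop the trial in weeks 4 to 12.* The death limits can. The gap concerns non-fatal toxicity only.
- *That later toxicity goes unmonitored.* It does not. Quarterly review is aimed at cumulative exposure, 5.5 removes patients for grade 4 non-hematologic or persistent grade 3 events, and 6.1 and 6.2 require holds. With about 1.4 patients on treatment at a time, serious events would be seen.
- *That mild early reactions would in practice halt accrual.* The documents do not establish this. The body text speaks of significant toxicities, and section 7 requires case report form entry only for grade 3 or higher events and serious events, so a literal any-grade count could not be made from those forms. If the 10% local and 5% constitutional reactions in 8.1.3 all fell within 10 days and were counted, the halt probability would be 0.13 (p = 10%, full overlap) to 0.26 (p = 15%, no overlap). No onset time is given for local reactions.

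One could also say that an early stopping rule need not cover the whole course. That is a legitimate choice, but the plan would then have to say that the 33% ceiling and the probabilities refer to early toxicity only.

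**Conclusion.** The point holds as a defect in the definition and window of the counted event. It is not an arithmetic error, and it is not an absence of safety monitoring. Applying the 11.2 definition to the 13.1 table is an inference, since 13.1 has no cross-reference, but no other definition exists.

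The size depends on event timing, which the documents do not give. At a 12-week rate of 33%, the halt probability by 18 patients falls from 0.79 to between 0.71 and 0.31 for early shares of 90% to 50%, and lower still if events are spread evenly. These are illustrations, not estimates for this regimen. The conflict over the threshold needs no timing assumption: it is worth 0.79 against 0.54 at 33%. The primary efficacy test is unaffected. The wording should be changed, because the gain in safety is real and the change is cheap.

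**What to change.** 1. Replace the 11.2 definition with one graded definition: any at least possibly related grade 4 event, or any at least possibly related grade 3 non-hematologic event that is unexpected or is thrombotic microangiopathy or line-associated thrombosis. Count from first dose to 30 days after the last protocol-specified IL-2 dose. Use that single term throughout 13.1.
2. Keep the 3-week assessment. Count later qualifying events when they occur, against the row for the number of patients treated at that time. The table ends at 18 of 24, so a limit for the last patients is needed to complete this. For example, 8 of 24 keeps the one-third proportion and moves the halt probability at 33% from 0.792 to 0.817.
3. Change the body text to halt when the count reaches or exceeds the limit, the rule that reproduces the table.
4. State that the table's probabilities refer to the rate over that window with complete follow-up, and that treatment-related deaths count over the same window.
5. In 12.1.3, extend the 5-business-day adverse event form timeline beyond day 60 to match.

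**Cost.** Wording in 11.2, 12.1.3 and 13.1. Grade 3 or higher events are already recorded to 30 days past the last IL-2 injection. Grade 1–2 and other expected grade 3 reactions would no longer count. A temporary halt for DSMC review becomes more likely at intermediate rates: 0.42 at a full-window rate of 20% and 0.58 at 25%. Raising each limit by one would cut these to 0.16 and 0.28, but that is the present body-text rule and gives only 0.54 at 33%. With a window of 84 + 30 = 114 days, about 6 × 114/365 = 1.9 patients would have incomplete follow-up at a look, against 6 × 21/365 = 0.35 with 21 days.

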#### 12.1.3 Data Collection Forms and Submission Schedule

All data will be collected on Medidata Rave®. Data will be stored in encrypted, password protected, secure computers that meet all HIPAA requirements.

Form	Submission Timeline
Eligibility Checklist	Complete prior to registration
On Study Forms	Within 10 business days of registration
Baseline Assessment Forms	Within 10 business days of registration
Treatment Forms	Within 10 business days of treatment administration
Adverse Event Report Forms	Within 5 business days, but only through day 60 (DLT period)
Response Assessment Forms	Within 10 business days of response assessment
Other assessment forms (e.g. concomitant meds, chemistry, hematology, neuro exam, physical exam)	Within 10 business days of the assessment
Off Treatment/Off Study Forms	Within 10 business days of completing treatment or being taken off study for any reason
Follow up/Survival Forms	Within 10 business days of the protocol defined follow up visit date or call

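### The stopping rule's text halts accrual one patient later than its own footnote and table, and the toxicity it counts has no stated grade

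*Combined protocol and SAP*

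**What the plan says.** **Trigger.** The section on safety analysis and stopping rules, under 13.1, gives limits of 2, 3, 4 and 6 patients at 6, 9, 12 and 18 treated. The text reads "If more than the specified number of patients has significant treatment related toxicities, patient accrual will be halted", followed by mandatory DSMC review before accrual may resume. Footnote 1 to the table reads "halt enrollment and evaluate if the cumulative # of patients reaches or exceeds the specified limits". The limit column is labelled as the number "of patients with unacceptable toxicity to halt enrollment". The text also says "The early stopping rule for safety/toxicity will be assessed for each patient after 3 weeks of treatment", and adds "These rules are in addition to the quarterly review of all toxicities submitted to the COH DSMC".

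**Counted event.** Section 11.2 defines unacceptable toxicity as "any toxicities that are at least possibly related to either ECP or IL-2 and occur during cycle 1 (within 10 days" of starting therapy). It gives no grade. Section 5.3 describes a single course: "IL-2 and ECP combination therapy will be given for 12 weeks". Section 7.2 requires case report form entry for adverse events of grade 3 or higher and for all serious adverse events. Other adverse events are monitored by the Protocol Management Team (PMT) and go into its report. The form schedule in 12.1.3 says of adverse event forms "Within 5 business days, but only through day 60 (DLT period"), although Section 5.9 states that a dose-limiting toxicity definition does not apply.

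**Infection.** Sections 6.1 and 6.2, on dose modification, state that infection on treatment is not considered related. Section 7.2 has the principal investigator attribute every event individually.

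**The concern.** A stopping rule has to give one answer for one set of data. Here, whenever the count equals the limit, the two sentences give opposite answers, and the less protective one is the sentence that sets out the halt and the DSMC review. This is the plan's only numerical toxicity limit. The quarterly review continues alongside it but carries no number.

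The event definition raises a second, smaller problem. Taken literally, Section 11.2 counts a mild injection-site reaction. The word *significant* in the stopping-rule text suggests something more severe. The two readings could produce different counts from the same patients, and the literal one counts events that need not appear on the case report form.

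**Working it through.** **Inputs, all from the stopping table.** Looks at n = 6, 9, 12, 18; limits b = 2, 3, 4, 6; true rates p = 15%, 33%, 45%; 12 printed cumulative probabilities.

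**Method.** Let X be the cumulative number of patients with the event. At each look, halt if X ≥ b (footnote) or X ≥ b + 1 (text). Carry forward only the paths that have not halted, add the binomial count from the next patients, and sum the halting probabilities.

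**Worked at p = 0.33, first look.**
- P(X = 0) = 0.67^6 = 0.0905
- P(X = 1) = 6 × 0.33 × 0.67^5 = 0.2673
- P(X = 2) = 15 × 0.33² × 0.67^4 = 0.3292
- Footnote: P(X ≥ 2) = 1 − 0.0905 − 0.2673 = 0.6422 (printed 0.64)
- Text: P(X ≥ 3) = 0.6422 − 0.3292 = 0.3130

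**Second look, footnote.** The surviving states are X = 0 and X = 1.
- From 0, three events in three patients are needed: 0.33³ = 0.0359.
- From 1, at least two are needed: 3 × 0.33² × 0.67 + 0.0359 = 0.2548.
- Added halting probability: 0.0905 × 0.0359 + 0.2673 × 0.2548 = 0.0714, giving 0.7136 (printed 0.72).

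Continuing in the same way:

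| Rate | Source | n = 6 | n = 9 | n = 12 | n = 18 |
|---|---|---|---|---|---|
| 15% | printed | 0.22 | 0.25 | 0.26 | 0.27 |
| 15% | footnote | 0.224 | 0.249 | 0.259 | 0.264 |
| 15% | text | 0.047 | 0.059 | 0.065 | 0.068 |
| 33% | printed | 0.64 | 0.72 | 0.75 | 0.80 |
| 33% | footnote | 0.642 | 0.714 | 0.753 | 0.792 |
| 33% | text | 0.313 | 0.407 | 0.468 | 0.536 |
| 45% | printed | 0.84 | 0.89 | 0.93 | 0.95 |
| 45% | footnote | 0.836 | 0.897 | 0.927 | 0.956 |
| 45% | text | 0.558 | 0.689 | 0.768 | 0.851 |

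The largest gap from print is 0.008 under the footnote and 0.327 under the text (0.313 against 0.64 at patient 6, 33%). Checking after every patient with the same stepped limits gives the same values at the tabulated n.

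**How often the readings conflict at patient 6.** They differ when exactly 2 of 6 have the event: 15p²(1 − p)^4 = 0.18, 0.33 and 0.28 at 15%, 33% and 45%.

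**Patients treated before a first halt at 33% (24 if none).**
- Footnote, with halting probabilities 0.6422, 0.0714, 0.0397 and 0.0385 at the four looks: 6 × 0.6422 + 9 × 0.0714 + 12 × 0.0397 + 18 × 0.0385 + 24 × 0.2083 = 10.7.
- Text, with 0.3130, 0.0935, 0.0616 and 0.0678: 6 × 0.3130 + 9 × 0.0935 + 12 × 0.0616 + 18 × 0.0678 + 24 × 0.4641 = 15.8.

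These means ignore the Simon stage 1 stop (2 or fewer responses in 9). Including it, and assuming response independent of toxicity, gives 8.5 against 11.2 at a 25% response rate and 10.3 against 15.1 at 50%. The difference is then 2.7 to 4.8 patients instead of 5.2 (15.82 − 10.66).

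**Event definition.** No probability can be attached to the missing grade, because the documents give no rate of related toxicity of any grade over the first 10 days.

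**The case against.** The strongest reply is that the conflict resolves on the page. The text sends the reader to the table for the detailed rules, and the column label, footnote and probabilities all agree. A halt is also a pause for DSMC review and does not end the trial. This stands to the extent that the intended rule can be identified and the correction is small. It does not remove the contradiction: staff who follow the halting sentence as written would continue accrual at a count where the footnote halts it.

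On the event, a reader might infer that the toxicity is undefined or has several competing windows. The documents do not support that. Section 11.2 defines the term once, with a 10-day window. The 3-week point is when the rule is assessed and could look back on those 10 days; day +21 concerns follow-up of ongoing toxicity; day 60 sits in a form-submission schedule. None is stated as a counting window.

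A reader might also infer that lower-grade events are not collected at all. Section 7.2 does route non-serious events to the PMT, which is responsible for implementing the stopping rules. The narrower gap remains: case report form entry is required only for grade 3 or higher and serious events, so a literal count cannot be made from the required forms alone.

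**Conclusion.** The stopping-rule text is wrong as written and needs correcting. At the 33% rate, which the section itself treats as too high, following the text would lower the chance of halting by patient 18 from 0.79 to 0.54; at 15% and 45% the change is from 0.26 to 0.07 and from 0.96 to 0.85. These figures assume independent patients with a common event rate and review at the tabulated counts. The table itself is sound: a reader might suspect its limits or probabilities, but they reproduce under footnote 1.

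The missing grade, the reference to a cycle and the mismatch in terms are real but secondary, and their effect cannot be sized from the documents. The infection wording is minor. It sits in the dose-modification sections, and the plan does not say how it bears on the stopping count.

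**What to change.** 1. In the stopping-rule text, replace *more than the specified number* with *reaches or exceeds the specified number*. The limits and printed probabilities do not change.
2. Use one term for the counted event in Section 11.2 and in the stopping-rule text, with a grade threshold chosen by the sponsor and the DSMC. State that 3 weeks is the assessment time, or that it is the window if that was intended.
3. Delete the reference to cycle 1 in Section 11.2 and the DLT label in the 12.1.3 form schedule.
4. Make the case report form capture whatever the rule counts.
5. Minor: reconcile the infection statements in 6.1 and 6.2 with the case-by-case attribution in 7.2 for the purpose of the count.

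The cost is a handful of wording changes and one decision on grade. Data collection grows only if the chosen grade is below 3.
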